# 5.5 Objectives and hypothesis

## 5.5.1 General Objective

To evaluate the safety and tolerability of the ophthalmic gel PRO-167 on the ocular surface.

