# 5.5.3 Hypothesis

*Ha* Ophthalmic gel PRO-167 presents a safety and tolerability profile similar to the comparator in healthy subjects.

Ho Ophthalmic gel PRO-167 presents a safety and tolerability profile different from the comparator in healthy subjects.

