## 6.4.3.2 Goblet cell density (Cytology per impression)

The density of goblet cells in the conjunctiva can be a reflection of the severity of alteration in the ocular surface. [39] It has been determined that the normal density is greater than 500 cel / mm2. [40] Impression cytology refers to the application of a cellulose acetate filter to the ocular surface to remove the superficial layers of the epithelium; these removed cells can be subjected to histological, immunohistological or molecular analysis. [41]

The cytology per impression of the conjunctiva will be done by the researcher using the device provided by the sponsor for this purpose, which may consist of a circular cell of approximately 10 mm in diameter, with a cellulose acetate filter millicell. After ocular surface anesthesia, with topical tetracaine, the researcher will ask the subject to expose the temporal surface of the eye to be evaluated and gently press the cell on the temporal conjunctiva (2 to 3 mm of the sclerocorneal limbus) for 5 seconds and remove the cell with a peeling technique (Illustration 1. Cytology per impression). Immediately fix with diethyl ether spray with one or two shots at 15 cm distance. The investigator will contact the Courier, within the first 24 hours, after the appointment designated by the sponsor for the shipment of the samples to histopathological analysis. You must complete the

requisition form provided by the investigator and attach it to the mailing. The format will consist of three sheets (1 original and 2 copies) which will be assigned as follows: original sheet for the Courier, 1 copy will be collected by the monitor and 1 copy will remain in the research center and will be filed in the corresponding folder to each research subject.

Illustration 1. Cytology per impression

The data of the histopathological report to be recorded in the CRF are: density of goblet cells and degree of squamous metaplasia according to the Nelson scale. (**See Table 5**)

In the visits required to perform this procedure, it will be done prior to the use of ocular surface stains.

Table 5. Nelson classification

Grade	Detail description of the epithelial cells	Characteristics of goblet cells
0	Small and round cells; Large nuclei, 1: 2 ratio with nuclear cytoplasm	Abundant goblet cells (> 500 cells / mm2), globose and oval with an intense PAS-positive staining of the cytoplasm.

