#### 6.4.3.4.1 Stains

Staining with green lysine and fluorescein

A drop of topical anesthetic will be instilled in the conjunctival cul-de-sac, then a second drop will be applied to the tip of the strip of green lysine and fluorescein and it will be allowed to slip towards the bottom of the sac. It is essential to quickly evaluate the staining, in sequence, first in the DO and then the OS, so that the observed patterns are equally bright. [19] See Annex 13.3 Oxford Scale

The value obtained according to the Oxford scale will be registered in the CRF.

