#### 6.6.1 Calculation of the sample size

Although there are no references on the calculation of the sample size in phase I studies, it was considered pertinent to perform it according to the presentation of adverse events referred by Christ T, in a randomized controlled trial of parallel groups, single blind, with randomization where

it was evaluated the efficacy and tolerance of a 5% dexpanthenol ophthalmic gel versus a 5% panthenol ointment in 48 subjects with corneal erosion, keratoconjunctivitis by UV radiation or similar conditions. The intervention consisted in the application of 1 cm of the gel and the ointment during 4 and 3 days, respectively. [20]

The percentage of good tolerance that was presented with the gel was 25%, so it is expected that no more than 10% of the subjects report a bad tolerance with the formulation proposed in this protocol.

The sample size was calculated using the formula for proportions

$$n = p (1 - p) \left( \frac{Z_{1-\alpha + Z_{1-\beta}}}{p - p0 - \delta} \right)^2$$

With a statistical confidence of 95% corresponding to the type I error, equal to 1.96, with a power of 80%, corresponding to the type II error, equal 0.84.

According to the previous calculation, the result is 19 subjects, which was increased by 20% for the probable losses. The total sample size required is 24 subjects. Therefore, each group will consist of 12 subjects, who will provide an eye for analysis.

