#### 8.3 Statistical methodology

#### 8.3.1 Analysis of primary and secondary outcome variables

The statistical analysis will be carried out by personnel of Sophia Laboratories. The statistical program SPSS version 19 (IBM Corporation, Armonk, NY, USA) will be used.

The designated personnel will be blinded to the intervention groups. The coding will be done using consecutive numbers for each intervention group.

The data will be collected and sorted in an excel sheet. Later they will be exported to the platform of the SPSS program. The variables will be categorized according to their nature.

The result of the continuous quantitative variables will be presented in measures of central tendency: mean, standard deviation and ranges. See Table 4. Scales to be used

The normal distribution of the results will be obtained by the Kolmogorov-Smirnov test.

The statistical analysis of the continuous **quantitative variables** to find significant differences (p) will be the following:

- Intra-group analysis: Wilcoxon rank test.
- Inter-group analysis: Mann-Whitney U test.

The level of difference to consider significance will be an alpha of 0.05 or less.

The result of nominal and ordinal qualitative variables will be presented in frequencies, proportions and percentages.

The statistical analysis to identify significant differences of the **qualitative variables** will be done creating 2x2 contingency tables and it will be carried out in the following way:

- Intra-group difference: McNemar or Pearson test.
- Difference between groups: test χ2 (Chi-square) of Pearson.

The level of difference to consider significance will be an alpha of 0.05 or less.

For the reporting of adverse events all eyes of those participants who were randomly assigned to an intervention group after the baseline visit will be considered. The results will be expressed in number of cases (eyes).

The final report of the results will be shown in tables or graphs, as appropriate.

It will be considered that the investigational drug is safe and tolerable when there are no clinical and statistical differences in all the variables of primary outcome, with respect to its comparator.

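### The verdict rule in section 8.3.1 counts a difference from the comparator in either direction and nothing else, so a detected advantage for PRO-167 counts against it and equal non-serious ocular harm in both arms passes.

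*Combined protocol and SAP*

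**What the plan says.** - **Verdict rule.** Section 8.3.1 calls the product "safe and tolerable when there are no clinical and statistical differences in all the variables of primary outcome, with respect to its comparator". It does not say which direction of difference matters, does not define a clinical difference, and sets no limit on what may happen within the PRO-167 arm.
- **Hypotheses.** Section 5.5.3 sets Ha that PRO-167 "presents a safety and tolerability profile similar to the comparator in healthy subjects" against Ho that it "presents a safety and tolerability profile different from the comparator in healthy subjects". The section 1 hypothesis also speaks of similarity. None of them has a direction.
- **Tests.** Section 8.3.1 compares arms by Mann-Whitney U and Pearson chi-square on 2x2 tables: "The level of difference to consider significance will be an alpha of 0.05 or less". It states no side. The same section plans within-group Wilcoxon and McNemar (or Pearson) tests but does not link them to the rule.
- **Objective.** Section 5.5.1: "To evaluate the safety and tolerability of the ophthalmic gel PRO-167 on the ocular surface". Most of the specific objectives in 5.5.2 concern changes under PRO-167 itself.
- **Primary variables.** There are seven. Section 6.4.1.1 lists goblet cell density, epithelial defects and adverse events. Section 6.4.1.2 lists burning, foreign body sensation, itching and the comfort index.
- **Absolute yardsticks elsewhere.** Section 6.4.3.2 gives a goblet cell norm: "It has been determined that the normal density is greater than 500 cel / mm2". Table 4 gives absent as the normal value for each symptom, and Annex 13.3 grades staining.

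**The concern.** The trial's conclusion rests on this one sentence. A non-directional rule treats significantly less burning on PRO-167 the same way as significantly more. A purely relative rule cannot tell two harmless gels from two gels that irritate the eye to the same degree.

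The label it awards, safe and tolerable, is absolute, and so is the general objective. Followed literally, the rule can withhold the label from a product that did better and grant it to one whose own arm clearly got worse.

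**Working it through.** **Inputs.** 12 subjects per arm with one eye each (6.6.1), 1:1 allocation (7.1), alpha 0.05 and uncorrected Pearson chi-square (8.3.1), seven primary variables (6.4.1.1 and 6.4.1.2). I take each symptom as present or absent, because 8.3.1 uses 2x2 tables. The documents give no event rates for these variables, so the rates and counts below are illustrations.

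**The plan's own figure.** The rule carries no number. For the arm size, 19/(1 − 0.20) = 23.75, which rounds up to 24, or 12 per arm; this reproduces. The 19 itself cannot be checked, because the formula in 6.6.1 contains a δ with no stated value.

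**1. A detected advantage fails.** PRO-167 0/12, comparator 4/12:

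χ² = 24 × (0×8 − 12×4)² / (12 × 12 × 4 × 20) = 24 × 2304 / 11520 = 4.8, p = 0.0285.

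With 1/12 against 6/12, χ² = 24 × (1×6 − 11×6)² / (12 × 12 × 7 × 17) = 86400/17136 = 5.04, p = 0.0247. Both are differences under 8.3.1, and both favour PRO-167.

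Exact enumeration over two binomials of size 12 gives the chance of such a failure on one variable:

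| Assumed true rate, PRO-167 v comparator | Significant in PRO-167's favour |
|---|---|
| 10% v 25% | 12% |
| 10% v 50% | 60% |
| 5% v 50% | 75% |

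**2. Equal harm passes.** For 6/12 v 6/12, 9/12 v 9/12 or 12/12 v 12/12, the difference is zero and p = 1.0. If all 12 PRO-167 subjects were free of the symptom at baseline and 9 had it later, an exact McNemar test within the arm gives 2 × 0.5⁹ = 0.004. The planned within-group analysis would show the change, but the rule does not use it.

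For goblet cells, suppose both arms lose 300 cells/mm² with SD 150 (assumed). In 4,000 simulated trials the Mann-Whitney test showed no difference in about 95%, and the within-arm Wilcoxon test detected the loss in essentially all.

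**3. Chance failure for identical products.** If one significant difference on any of the seven variables is enough, and the tests are independent and of full size:

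- any difference: 1 − 0.95⁷ = 0.302
- at least one difference against PRO-167: 1 − 0.975⁷ = 0.162
- failures due only to differences in its favour: 0.302 − 0.162 = 0.139 (from unrounded values), or 46% of all failures.

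The actual size of the chi-square test at 12 v 12 depends on the event rate: 0.2% at 5%, 1.5% at 10%, 4.4% at 25% and 6.4% at 50%. Rare events therefore pull the 30% down, and rates near 50% push it slightly up. Positive correlation among symptoms lowers it.

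**4. What 12 eyes can show.** With 0 of 12 events the exact upper 95% limit is 1 − 0.025^(1/12) = 0.265, reported as 26% (0.2646). With 9 of 12 the exact 95% interval is 43% to 95%.

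**The case against.** **Similarity may be the real aim.** Both gels are 5% dexpanthenol with the same posology (6.3.1.1, 6.3.1.2), and the hypotheses speak of similarity, so a two-sided comparison is coherent. That stands for a claim of similarity. It does not stand for the label safe and tolerable, which the rule attaches to it.

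**Clinical and statistical may mean both.** The wording allows it. A better PRO-167 would then fail only when its advantage is also judged clinical, and the 30% would be lower. The faults remain: a large advantage still fails and equal harm still passes.

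**Other safeguards exist.** A reader might infer that the protocol has no answer to shared harm. That goes too far. Section 9.2 considers early termination when serious adverse events exceed 5% in each group, and one of 12 is already 8.3%. Section 8.3.2 plans an interim safety look, and the within-group tests would be reported. Shared non-serious harm, such as staining, goblet cell loss or burning, still does not affect the verdict.

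**Power is low.** A reader might infer that a better-tolerated PRO-167 would usually fail. At 12 per arm a modest advantage (10% v 25%) is significant only about 12% of the time, so it usually passes.

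**Shared harm is hypothetical.** The documents describe dexpanthenol as well tolerated (5.4). The equal-harm cases show what the rule permits; they do not predict that it will happen.

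**Conclusion.** The rule is wrong as written and should be fixed. The two faults follow from its wording and need no assumed rates: a detected advantage counts against PRO-167, and equal non-serious harm does not count at all. The trial is exploratory and all the data would still be reported, so what is at risk is the conclusion drawn from them, not their collection.

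The size is bounded. The 30% chance failure for identical products assumes seven independent tests of full size, any single significant difference being enough, and no separate clinical requirement. A higher or narrower figure would need event rates and correlations that the documents do not give.

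A reader might also take the 95% pass rate under shared goblet cell loss as the chance that the whole rule passes. It applies to one variable. Across seven independent variables of full size it would be 0.95⁷ = 70%.

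Nor does the untreated left eye serve as a full control. Staining is read "first in the DO and then the OS", so left-eye staining is available, but section 6.4.3.2 samples only the eye under evaluation and specifies no left-eye goblet cell specimen.

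**What to change.** 1. **Direction.** Reword 8.3.1 so that only a difference unfavourable to PRO-167 counts against it. Restate the hypotheses in section 1 and section 5.5.3 to match (not worse than the comparator); otherwise the rule and the hypotheses will contradict each other.
2. **Relative conclusion.** State it as no unfavourable difference from the comparator having been detected. Step 1 alone makes the rule easier to pass, and a non-significant result at 12 per arm is not evidence of non-inferiority. Even an assumed margin of 0.30 with 10% events in both arms needs 2 × 0.09 × (1.96 + 0.84)² / 0.30² = 15.7, so 16 per arm, for 80% power at one-sided 0.025.
3. **Own-arm table.** Base any statement about PRO-167's own safety on a pre-specified table of PRO-167 eyes moving from normal to abnormal on the protocol's own limits: goblet cells to 500/mm² or below, a rise in Oxford grade, a symptom newly present. For each limit, take as denominator the eyes that could make that move, since 6.2.1 sets no goblet cell requirement at entry. Give exact 95% intervals, and add the within-arm changes already planned, including the comfort index. Show left-eye staining for context.
4. **Limit.** If the table is to be a pass/fail condition, the sponsor must state the acceptable limit before unblinding. Without one, the table is descriptive.

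**Cost.** A few sentences in 8.3.1, matching edits to the two hypothesis statements, and one table; no new visits, subjects or measurements. The claim becomes more modest: even 0 of 12 leaves an upper 95% limit of 26%. That uncertainty is already present, and the current rule hides it.

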#### - Contact lens users.

#### 6.2.2.2 Medical and therapeutic criteria

#### 6.2.3 Elimination criteria

- Withdrawal of the consent letter under information.
- Presentation of a serious adverse event.
- No tolerability or hypersensitivity to any of the compounds used during the tests (fluorescein, green lysine, tetracaine)
- No tolerability or hypersensitivity to any of the investigational drugs.
- Adherence <50% determined by the diary of the subject.

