#### 6.3.2.1 Procedure to monitor adherence

Before delivering the medication to the research subject, the pharmacist must weigh the tubes to be delivered. After the return of the medication by the subject will also carry out the weighing. Guidelines to follow for weighing:

- o The pharmacist will use the scale provided by the sponsor
- o Place the tube in the center of the balance. You will get the result of the measurement.
- o It will remove the tube from the balance and put it back, confirming that the measurement is the same. If it is different, it will weigh one more time and take the average of the 3 measurements
  - o Record the result in the log and the CRF provided by the sponsor

Adherence to the intervention will be calculated considering: the weight of the empty tube, the weight of the strip, the weight of the tube with the content, the calculation of the total gel to be applied during the entire intervention time and the total weight of the applied gel . The following simplified formula will be used:

$$Ad = \frac{\left(P_i - P_f\right)100}{P_T}$$

Where:

Ad = adhesion

 $P_i$  = weight of the tube delivered to the subject at the start

 $P_f$  = weight of the tube returned by the subject

 $P_T$  = weight of the posology indicated for the intervention

$$P_T = (P_g)G$$

where:

 ${\it P_g}$ = weight of a 1 cm strip of the intervention, determined by the research and development department

G = number of applications indicated for the intervention

Adherence will be estimated at each visit where the research subject returns the intervention. Only tubes without apparent physical damage will be considered for the calculation. This result will allow the PI to determine if the subject continues in the study according to the stipulations of the elimination criteria.

The evaluation of the adherence by means of the diary of the subject will be carried out in the following way:

$$Ad = (A_r)100/A_i$$

Ad = Adhesion

 $A_r$ = Registered applications

 $A_i$ = Applications indicated for the intervention

The final (overall) adhesion will be determined by the average of the adherence of each of the visits.

It will not be considered for the calculation of final adherence if the subject did not return the tube in two subsequent visits.

Sophia Laboratories A.S. of V.C.

Version: 1.0

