Those subjects who comply with an adherence greater than 60% will be included in the statistical analysis to meet the objective of the study. It was considered that from the minimum dose necessary to obtain a pharmacological effect (reepithelizer / 1 cm per day) and the presence of adverse events (exposure) is sufficient to meet the overall design objective, according to the pharmacological characteristics of the product in investigation.

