#### 8.3.3 Population analysis and management of missing data

An analysis will be carried out by intent to treat where the data of the participants that have fulfilled two visits will be included (Basal Visit and visit 1).

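### The set tied to the safety and tolerability objective is selected on adherence above 60%: it can leave out early intolerance stops, is not ranked against the intent-to-treat set, and has no scoring rule for early stops

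*Combined protocol and SAP*

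**What the plan says.** Section 8.3 describes three populations.

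- For adverse events, section 8.3.1 states that "all eyes of those participants who were randomly assigned to an intervention group after the baseline visit will be considered".
- For the analysis that serves the study objective, the last paragraph of section 8.3.1 states: "Those subjects who comply with an adherence greater than 60% will be included in the statistical analysis to meet the objective of the study". Section 5.5.1 gives that objective as safety and tolerability.
- Section 8.3.3 adds: "An analysis will be carried out by intent to treat where the data of the participants that have fulfilled two visits will be included". The two visits are the Basal Visit and Visit 1. No purpose or rank is given. The heading mentions missing data, but the section states no rule for them.

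The decision rule, also in section 8.3.1, reads: "It will be considered that the investigational drug is safe and tolerable when there are no clinical and statistical differences in all the variables". It continues to the primary outcomes against the comparator and names no set in its own sentence.

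Two elimination criteria in section 6.2.3 bear on this: "No tolerability or hypersensitivity to any of the investigational drugs" and "Adherence <50% determined by the diary of the subject". Section 6.3.2.1 gives a tube-weight formula and a diary formula for adherence, and ties the returned-tube result to whether the subject continues. For the overall value it states: "The final (overall) adhesion will be determined by the average of the adherence of each of the visits".

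**The concern.** The set nearest to governing the tolerability conclusion is chosen on a variable that poor tolerability lowers. A subject whose eye burns and who stops early is the subject the tolerability variables are meant to capture, and is also among those most likely to fall below 60%. Elimination for intolerance acts on the same people, and the plan does not say whether the data they gave before leaving are used.

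The decision needs no difference in all primary variables, so who is analysed can decide it. With 12 subjects per group, each is 1/12 = 8.3% of an arm. Two analysts, one following the adherence paragraph and the other section 8.3.3, could analyse different subjects and each be within the plan.

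**Working it through.** **1. The sets side by side.**

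| Set | Section | Stated use | Early intolerance stop |
|---|---|---|---|
| All randomised | 8.3.1 | Adverse events | In |
| Adherence above 60% | 8.3.1, last paragraph | Study objective | In or out, see step 2 |
| Basal Visit and Visit 1 attended | 8.3.3 | None stated beyond the intent-to-treat label | In if Visit 1 was attended, even after stopping; otherwise out |

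No text ranks the second set against the third.

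**2. Can the 60% cut exclude an early stop?**

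Inputs from the documents:
- 4 applications a day for 10 days (Summary), so 4 × 10 = 40 due.
- Treatment starts on day 1, the day after the Basal Visit (6.5.1.2).
- Visit 1 is on day 3 ± 1 (6.4.4).
- Overall adherence is the average of the visit values (6.3.2.1).

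Assumptions: every strip is applied until the stop; all later applications still count as due; Visit 1-day strips belong to the first interval; both visits yield a value.

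Let n2 be the applications due after Visit 1 and k those made after it. For a stop on or after the Visit 1 day, overall adherence = 100 × (1 + k/n2)/2.

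Visit 1 on day 3 (12 due, then 28):

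| Stop after | k | Overall adherence | Above 60%? |
|---|---|---|---|
| Day 3 | 0 | (1 + 0/28)/2 = 50.0% | Out |
| Day 4 | 4 | (1 + 4/28)/2 = 57.1% | Out |
| Day 5 | 8 | (1 + 8/28)/2 = 64.3% | In |
| Day 6 | 12 | (1 + 12/28)/2 = 71.4% | In |

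The boundary moves within the visit window:
- Visit 1 on day 2 (8 due, then 32): a stop after day 3 gives (1 + 4/32)/2 = 56.3%, out; after day 4, (1 + 8/32)/2 = 62.5%, in.
- Visit 1 on day 4 (16 due, then 24): a stop after day 5 gives (1 + 4/24)/2 = 58.3%, out; after day 6, (1 + 8/24)/2 = 66.7%, in.

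Now change only the scoring. Take the day-4 stopper with Visit 1 on day 3, at 57.1% above. If the only value available is the one from Visit 1, the score is 12/12 = 100%. If applications after the stop are not counted as due, it is again (12/12 + 4/4)/2 = 100%. The same subject is out under one reading and in under two others, and the plan does not choose.

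**3. Which measurement feeds the cut?** Section 6.2.3 uses the diary for its adherence criterion. Section 6.3.2.1 ties the returned-tube result to the elimination criteria. The 60% paragraph names neither.

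**4. What data would be left unused?** By the schedule in section 6.5, ocular symptoms and epithelial defects are recorded at Visit 1. The diary, returned at Visit 1 and the final visit, holds the symptoms after each application (6.4.3.9). Goblet cell density and the comfort index have no post-baseline value before the final visit. So an exclusion discards existing data on burning, foreign body sensation, itching and epithelial defects; for the other two variables an early leaver has nothing to discard.

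**The case against.** Much of the case on the other side stands.

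- **A set is tied to the objective.** A reader might infer that the plan names no set at all for its conclusion. The decision sentence does not, but the paragraph after it links the adherence set to the objective, and adverse events have their own set. What is missing is the rank against section 8.3.3 and a set that is not selected on tolerability.
- **The plan does define overall adherence.** From "the calculation of the total gel to be applied during the entire intervention time" a reader might infer a whole-course denominator, which would push the cut later. Overall adherence is stated as the average of visit values, and the two cannot be combined: a perfectly adherent subject would score (12/40 + 28/40)/2 = 50%. The whole-course reading should not be used.
- **Safeguards exist.** Section 8.3.3 asks for attended visits, not continued treatment, so someone who stops on day 1 and attends Visit 1 stays in that set. Withdrawal of product is recorded with an adverse event (9.3.1.1), and leavers who cannot be seen are asked about events and their reason (8.1.1). None of this fixes the set for the symptom variables and epithelial defects.
- **Two apparent inconsistencies are not errors.** Elimination below 50% and analysis above 60% serve different purposes and may differ. The remark on a minimum daily amount is not presented as the derivation of 60%.
- **Exposure is a legitimate consideration.** Under a similarity hypothesis, adding barely exposed subjects can also dilute a difference. That supports keeping the adherence set, but as a supportive analysis.

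**Conclusion.** The point holds and should be fixed. Followed as written, the adherence paragraph can remove early intolerance stops from burning, foreign body sensation, itching and epithelial defects although data exist. The plan leaves open which set prevails, which adherence source applies, how early stops are scored, and whether eliminated subjects' data count.

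The claim is that this can happen, not that it will. The day-by-day results rest on the assumptions in the working, full dosing before the stop and all later applications counted as due; other scoring choices keep the same subject in.

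A reader might also infer that the selection must favour PRO-167. The documents do not support that. They give no rate of intolerance stops by arm, so neither the size nor the direction of any bias can be computed. Adverse event reporting is not affected.

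**What to change.** - State that the safe-and-tolerable rule is judged, for every primary safety and tolerability variable, on all randomised subjects with at least one application, analysed as randomised, using all data up to discontinuation, including data from eliminated subjects.
- Keep the set above 60% as supportive only, with one adherence source (weight or diary) and one scoring rule for early stops and for subjects with a single visit value.
- Report by arm, with reasons, withdrawals for intolerance and missing final-visit goblet cell density and comfort index.
- Reconcile sections 6.2.3, 6.3.2.1, 8.3.1 and 8.3.3 on whose data are analysed. No clinical withdrawal rule need change.

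The cost is protocol wording: symptom grades, diary, epithelial defects, adverse events and reasons for leaving are already collected. There are two downsides. Subjects with little exposure enter the primary set and may dilute a difference, which the supportive set would help to show. And nothing is recovered for goblet cell density or the comfort index in early leavers.

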#### Final Visit / Day 11.

It can be done in a period ± 1 day in relation to the 11th day of the start of application.

- 1. Visual ability
- 2. Density of goblet cells (Cytology per impression)
- 3. Intraocular pressure.
- 4. Eye comfort index
- 5. Evaluation of ocular signs and symptoms
- 6. Integrity of ocular surface
  - a. Epithelial defects (TF and TVL)
  - b. TRL
- 7. Subsequent segment evaluation.
- 8. Vital signs
- 9. Return and evaluation of quality questionnaire.
- 10. Evaluation of adverse events

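### The over-60% adherence filter has no exception for subjects stopped for harm, and the plan does not say which analysis set decides that the gel is safe and tolerable

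*Combined protocol and SAP*

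**What the plan says.** Section 8.3.1 ties the analysis that answers the study objective to adherence: "Those subjects who comply with an adherence greater than 60% will be included in the statistical analysis to meet the objective of the study". The sentence after it argues that this much exposure is enough. It does not create an exception.

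The same section gives the decision rule. The product is "safe and tolerable when there are no clinical and statistical differences in all the variables of primary outcome", relative to the comparator. Sections 6.4.1.1 and 6.4.1.2 list seven primary variables: goblet cell density, epithelial defects and adverse events for safety; burning, foreign body sensation, itching and the comfort index for tolerability.

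The elimination criteria in section 6.2.3 include "Presentation of a serious adverse event" and "No tolerability or hypersensitivity to any of the investigational drugs".

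Two other provisions set a population. Section 8.3.1 has a separate rule for adverse events: "For the reporting of adverse events all eyes of those participants who were randomly assigned to an intervention group" are counted. Section 8.3.3 describes an intent-to-treat analysis in which "the data of the participants that have fulfilled two visits will be included (Basal Visit and visit 1" are the two visits required. That analysis has no adherence condition.

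On computing adherence, section 6.3.2.1 gives a weight formula and a diary formula, and adds: "The final (overall) adhesion will be determined by the average of the adherence of each of the visits".

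**The concern.** A subject who reacts badly and is taken off the gel stops applying it. Measured against the full course, that subject's adherence is low because of the reaction. A filter on adherence then selects on a consequence of treatment. Under the decision rule, finding no difference is the favourable result, so removing reactors from an arm pushes towards the conclusion the sponsor hopes for.

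The intent-to-treat set in section 8.3.3 would keep a subject who attended visit 1 and then stopped, but nothing ranks it above the over-60% set, which is the one tied to the study objective. It also omits anyone who stops early and misses visit 1. At stake is whether the primary tolerability comparison includes the subjects who tolerated the gel worst. If the deciding set is left open, it could be chosen after the data are seen.

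**Working it through.** **Inputs.** Four applications a day (section 6.3.1) for 10 days (section 1), so 4 × 10 = 40 applications. Visit 1 on day 3 ± 1 (section 6.4.4). 12 subjects per arm, and no more than 10% expected to report bad tolerance (section 6.6.1). Alpha 0.05 and Pearson chi-square between groups (section 8.3.1). The plan gives no figure of its own for the filter's effect.

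**1. Which variables can the filter remove?** Epithelial defects and the three symptoms are assessed at visit 1 and at the final visit. After baseline, goblet cell density and the comfort index are scheduled only at the final visit (sections 6.4.4 and 6.5). A stopped subject who does not attend that visit lacks those two values with or without the filter. For such a subject the filter's own effect is on four variables.

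**2. Which stops fail the filter?** Assume full dosing up to a stop at the end of day d.

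- *Full course as denominator:* 4d/40. Day 6 gives 24/40 = 60.0%, which is not above 60%, so it fails. Day 7 gives 28/40 = 70% and passes.
- *Average of two visits, visit 1 after v dosing days, d ≥ v:* [100 + 100(d − v)/(10 − v)]/2.

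| v | last failing stop | next day |
|---|---|---|
| 2 | day 3: 56.2% | day 4: 62.5% |
| 3 | day 4: 57.1% | day 5: 64.3% |
| 4 | day 5: 58.3% | day 6: 66.7% |

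- *Visit 1 alone, three dosing days:* day 1 gives 1/3 = 33.3% and fails; day 2 gives 2/3 = 66.7% and passes.
- *Indicated applications end at the stop:* adherence is 100%, so nobody fails.

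**3. How often?** Let s be the share of the 10% with bad tolerance who stop (assumed 25%, 50% or all). The chance of at least one intolerance stop in an arm is 1 − (1 − 0.10s)^12. If stops fall evenly over 10 days (assumption), the chance of at least one by day k is 1 − (1 − 0.10s × k/10)^12.

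| s | any stop | by day 4 | by day 6 |
|---|---|---|---|
| 25% | 26.2% | 11.4% | 16.6% |
| 50% | 46.0% | 21.5% | 30.6% |
| 100% | 71.8% | 38.7% | 52.4% |

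**4. Effect on a yes/no symptom.** Smallest number of PRO-167 cases among 12 that gives p ≤ 0.05 (Pearson, no continuity correction). The counts are illustrative, and dropped subjects are PRO-167 cases.

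| comparator cases | none dropped | one dropped | two dropped |
|---|---|---|---|
| 0 | 4 (p = 0.0285) | 5 (4/11, p = 0.0215) | 5 (3/10, p = 0.0412) |
| 1 | 6 (p = 0.0247) | 6 (5/11, p = 0.0428) | 7 (5/10, p = 0.0289) |
| 2 | 7 (p = 0.0350) | 8 (7/11, p = 0.0211) | 8 (6/10, p = 0.0354) |
| 3 | 8 (p = 0.0405) | 9 (8/11, p = 0.0221) | 9 (7/10, p = 0.0348) |

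A single exclusion can change the result: 4/12 v 0/12 gives p = 0.0285, while 3/11 v 0/12 gives p = 0.0524. With one comparator case, a single drop leaves the required count at 6.

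**The case against.** The best defence is that the plan already covers most of this. Section 8.3.3 is the section on analysis populations, and its set has no adherence condition. Adverse events are primary, are reported for all randomised eyes and enter the decision rule, and an intolerance that ends treatment would be expected to appear there. The rule also asks for no clinical difference, so a non-significant p-value is not sufficient by itself. The comparator has the same active ingredient, strength and posology, and its reactors pass through the same filter. All of this limits the harm. None of it says which set decides, and section 8.3.3 still omits a reactor who misses visit 1.

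The denominator is also open to argument. If the indicated applications end when the investigator stops treatment, a compliant reactor scores 100% and stays in. Section 6.3.2.1 refers to the gel due over the entire intervention time, which points the other way, but the reading is possible and belongs in the range.

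Three stronger readings are tempting, and the documents do not support them:

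- **Reactors vanish from the safety evaluation altogether.** They do not, because adverse-event reporting ignores adherence.
- **The filter strips all six other primary variables.** Goblet cell density and the comfort index are affected only if a stopped subject attends the final visit.
- **The 26%, 46% and 72% measure the problem.** They count any intolerance stop on any day, including stops late enough to pass the filter.

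**Conclusion.** The point holds as a gap that should be closed. The plan ties the objective to a set that can exclude subjects because they were harmed, in a trial where no difference is the favourable result, and it does not say whether that set or the intent-to-treat set governs. The loss falls mainly on epithelial defects, burning, foreign body sensation and itching.

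The size is modest. The last failing stop ranges from day 6 to none at all, depending on how adherence is read. The chance of at least one filter-failing stop in an arm runs from about 11% to 52% over stops by day 4 to day 6, and is lower under the visit-1-only reading and zero if the denominator ends at the stop. These figures rest on the 10% ceiling in section 6.6.1, on assumed stopping shares and on evenly spread stops; reactions that cluster early would raise them. With one or two reactors dropped from PRO-167 and none from the comparator, the bar rises by at most one case. Confidence is medium, because the outcome depends on which reading of adherence the sponsor intends.

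**What to change.** In section 8.3.1, state that the primary safety and tolerability variables are analysed, and the safe-and-tolerable decision made, in all randomised subjects with any available post-baseline data, regardless of adherence and of the two-visit condition in section 8.3.3. Report the over-60% set as a sensitivity analysis.

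The cost is a change of wording. It adds no visit, measurement or subject. The downside is that some low-exposure subjects enter the deciding set, which may dilute differences slightly; the sensitivity analysis will show whether that matters.

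Requiring final-visit assessments of eliminated subjects is not recommended as a remedy for this bias. After an early stop, the day 11 goblet cell value would be taken well off drug, and the comfort index asks about the past week, so recovered values could themselves favour no difference.
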